7.2.1.6 Reporting of Serious Adverse Events

All SAEs occurring up to 30 days following completion of or discontinuation from the study must be reported to the sponsor, regardless of whether they are suspected of having a causal relationship with the study drug. Any SAEs for which the investigator does suspect a causal relationship must be reported to the sponsor regardless of the time elapsed since the last dose of the study drug.

Patients will be instructed to report SAEs to the investigator **within 24 hours**, by telephone. In turn, the investigator must report all SAEs to the sponsor **within 24 hours** of occurrence or notification by the patient, using the sponsor's SAE form. The sponsor will provide contact information for reporting SAEs. An assessment of causality must be provided at the time of the initial report. The investigator or delegate must then complete and submit a follow-up SAE form to the sponsor **within 5 calendar days**, and must submit further follow-up forms if additional relevant follow-up information becomes available.

The sponsor will submit reports of SAEs to the appropriate regulatory agencies, in line with local regulatory requirements and timelines.

Investigators must report all SAEs to their IRB/IEC as well as to the sponsor. If any SAE that is considered at least possibly related to the study medication and is unexpected occurs at one site, the sponsor will promptly inform all other sites of this, and all investigators must then report this event to their own IRBs/IECs, following the same timelines as above or following local IRB/IEC policy, whichever takes precedence.

7.2.1.7 Follow-up and Documentation of SAEs

SAEs that occur during the study and up to 30 days after the last dose of study drug must be documented in the patient's medical record and on the SAE report form. The investigator should attempt to establish a diagnosis of the event based on signs, symptoms, and/or other clinical information. In such cases, the diagnosis rather than the individual signs/symptoms should be documented as the SAE.

All SAEs must be followed until resolution, the condition stabilizes, the event is otherwise explained, or the patient is lost to follow-up. The investigator is responsible for ensuring that follow-up includes any supplemental investigations that may be indicated, in order to elucidate the nature and/or causality of the SAE as completely as possible. This may include additional laboratory tests or investigations, histopathological examinations, or consultation with other health care professionals. The sponsor may request that the investigator perform or arrange for the conduct of supplemental measurements and/or evaluations.

If a patient dies during participation in the study or during a specified follow-up period, the sponsor should be sent a copy of any post-mortem findings, including histopathology.

New or updated information is to be recorded on the originally completed SAE report form, with all changes signed and dated by the investigator.

The clinical research associate (CRA) will verify the original SAE report form against the source documents at the next monitoring visit.

7.2.1.8 Adverse Events of Special Interest

7.2.1.8.1 Neutropenia

Patients taking deferiprone must be monitored for neutropenia, defined as a confirmed absolute neutrophil count (ANC) less than 1.5×10^9 /L. Categories of neutropenia are as follows:

• Mild: A confirmed ANC $< 1.5 \times 10^9/L \text{ but } \ge 1.0 \times 10^9/L$

• Moderate: A confirmed ANC $< 1.0 \times 10^9/L \text{ but} \ge 0.5 \times 10^9/L$

• Severe: A confirmed ANC $< 0.5 \times 10^9$ /L. Severe neutropenia is also

referred to as agranulocytosis.

For a case of neutropenia to be confirmed, there must be 2 consecutive counts, a maximum of 3 days apart, that are both less than the specified value. If both counts are below 1.5×10^9 /L but are not in the same severity category, a third count will be required to determine the severity.

The management of different severities of neutropenia is described below. In addition to having ANC monitored, patients or authorized legal guardians will be advised to immediately report any symptoms indicative of infection such as fever, sore throat, and flulike symptoms; and will be provided with an emergency services card with contact information which they are advised to carry with them at all times. In presence of confirmed fever and/or infection, they will be required to have their neutrophil counts tested as soon as possible and no later than 24 hours after the symptoms of infection are detected.

Mild neutropenia: The patient should continue deferiprone treatment, and ANC will be monitored every 2 days until resolution of the event, defined as 2 consecutive ANC ≥ 1.5 x 10^9 /L. If ANC is still < 1.5 x 10^9 /L after 14 days, the investigator is to do the following:

- Withdraw patient from the study and monitor him/her until resolution of the event
- Advise patient regarding protective isolation
- Examine patient the same day (if possible), including drug history and physical examination
- Notify ApoPharma Inc. by fax

If a patient with mild neutropenia develops an infection, deferiprone therapy must be interrupted immediately, and neutrophil count will continue to be monitored every 2 days

until resolution. Therapy can be re-initiated once all symptoms have been resolved and it is deemed safe by the investigator.

Moderate neutropenia: Patient will immediately interrupt treatment, and ANC will be monitored every 2 days until resolution of the event. If ANC is still $< 1.5 \times 10^9$ /L after 14 days, the investigator is to do the following:

- Withdraw patient from the study and monitor him/her until resolution of the event
- Provide protective isolation; if clinically indicated, admit patient to hospital and obtain vital signs every 4 hours
- Examine the patient the same day, if possible, including drug history and physical examination
- If possible, obtain viral studies (CMV, parvovirus, hepatitis A/B/C), serum ALT, BUN, creatinine, and 10 mL serum split into two 5-mL aliquots for frozen storage, for future analysis
- Notify ApoPharma Inc. by fax

Severe neutropenia/agranulocytosis: Patient will immediately discontinue treatment and will be permanently withdrawn from the study, and ANC will be monitored daily until resolution of the event. The following procedures should be done by the investigator or the treating physician, as appropriate:

- Provide protective isolation; if clinically indicated, admit patient to hospital and obtain vital signs every 4 hours
- Examine the patient the same day, if possible, including drug history and physical examination
- If possible, obtain viral studies (CMV, parvovirus, hepatitis A/B/C), serum ALT, BUN, creatinine, and 10 mL serum split into two 5-mL aliquots for frozen storage
- With the patient's consent, collect a blood sample to attempt to identify genetic or other biomarkers related to agranulocytosis (refer to the operations manual for further instructions)
- If possible, consider obtaining bone marrow aspirate for:
 - Histology
 - Progenitor culture

- o Frozen storage (1 mL sample)
- If possible, consider obtaining bone marrow biopsy (minimum length 3 mm)
- Perform septic work-up including chest X-ray, blood, urine and throat cultures
- Obtain q4h temperatures from patient (monitored by family at home if patient is not in the hospital)
- If warranted, administer granulocyte stimulating factors, such as G-CSF 10 μ g/kg, as an inpatient if possible, beginning the same day that the ANC is confirmed as < 0.5 x 10^9 /L; administer daily until ANC is > 1.5 x 10^9 /L on 2 consecutive days
- If ANC $< 0.5 \times 10^9$ /L for 7 days, repeat bone marrow biopsy and aspirate weekly during the period of agranulocytosis, if warranted
- Notify ApoPharma Inc. by [contact] Infections

If the patient develops fever or any type of infection during the study, deferiprone must be interrupted immediately and neutrophil count should be obtained and monitored more frequently (every 2 days if ANC $<1.5 \times 10^9$ /L). Patients should be advised to report immediately to their physician any symptoms indicative of infection such as fever, sore throat, and flu-like symptoms. Patients will be provided with an emergency services card with contact information, and the patient/legal guardian will be advised to carry this card at all times. In presence of confirmed fever and/or infection, they will be required to have their neutrophil counts tested as soon as possible and no later than 24 hours after the symptoms of infection are detected. Therapy with deferiprone can be re-initiated once all symptoms have been resolved and it is deemed safe by the investigator.

7.2.2 Laboratory Measurements

Analyses will be performed at a central laboratory, with the exception of the weekly, biweekly, or monthly hematology assessments which may be performed at a local laboratory. Investigators must interpret each report promptly (preferably within 24 hours) and must document their review by signing or initialing and dating it. Any laboratory values that fall outside a clinically accepted range, or values that differ significantly from previous values, must be assessed for clinical significance, and must be marked by the investigator as either "CS" (clinically significant) or "NCS" (not clinically significant). Any clinically significant abnormalities or changes that are not part of a larger medical condition that is already

recorded must be further explained on the laboratory report and documented as an adverse event in the eCRF.

The following laboratory tests will be performed:

- **Hematology** (for Group 1, monthly throughout the study; for Group 2, weekly for the first 6 months, biweekly for the next 6 months, and monthly thereafter): hemoglobin, total WBC count, ANC, and platelet count
- **Biochemistry** (semi-annually; Visits 1, 3, 5, 7, and 9): total protein, GGT, lactate dehydrogenase (LDH), sodium, potassium, chloride, fasting glucose, total and direct bilirubin (indirect bilirubin will be calculated by the sponsor), AST, ALT, albumin, blood urea nitrogen, calcium, creatinine, uric acid, alkaline phosphatase, and amylase
- Serology (Visits 1 and 9): Hepatitis B and C and HIV testing
- **Urinalysis** (annually; Visits 1, 5, and 9): pH, specific gravity, glucose, protein, ketones, blood, and (if indicated by the dipstick results), sediment microscopy. If there is blood in the urine or three or more "plus signs" for protein, samples must be sent for microscopy.
- **Pregnancy** (quarterly; Visits 1–9): serum pregnancy test

7.2.3 Other Safety Measurements

7.2.3.1 Physical Examination

At Visits 1, 5, and 9, the investigator or a qualified delegate will perform a physical examination of the following organs and systems: head, ears, eyes, nose, throat and neck, respiratory system, cardiovascular system, gastrointestinal system, musculoskeletal system, central and peripheral nervous system, skin, thyroid, and general constitution.

7.2.3.2 Vital Signs

Temperature, heart rate, respiration rate, and systolic and diastolic blood pressure will be measured at each visit.

Weight will be measured at each visit, and height will be measured at Visits 1, 5, and 9.

7.2.3.3 Electrocardiogram

A standard 12-lead ECG will be performed at Visits 1, 5, and 9. As a minimum, the following parameters will be assessed: HR, PR, QRS, QT, QTcF, QTcB. The results will be interpreted by the investigator, and the overall interpretation will be documented.

7.2.3.4 Concomitant Medications

Information about prior and concomitant medications will be collected at each visit. The following must be recorded in the source documents and eCRFs:

- Any medications that the patient continues to take during the trial
- Any medications that the patient starts to take during the trial

The name, dose, route, frequency, indication, and start and stop dates of all medications used during the trial, as well as whether or not the medication was used to treat an adverse event, must be noted in the source documents and eCRFs.

7.2.4 Procedures in Case of Pregnancy

If a patient becomes pregnant during the course of the study, she will be immediately withdrawn. The pregnancy will be immediately reported to the sponsor, and information about the pregnancy is to be recorded on the appropriate form and in the patient's CRF. The patient will be followed to determine the outcome, and any premature termination of the pregnancy will be reported. Upon delivery, the child will be examined for any adverse symptoms or congenital anomalies. Follow-up information on the status of the mother and child will be forwarded to the sponsor no later than 8 weeks following the delivery.

If the partner of a male patient becomes pregnant during the course of the study, or if the fetus may have been exposed to the patient's study products either through maternal exposure or through transmission via semen following paternal exposure, the pregnancy must be reported to the sponsor, and information about the pregnancy must be recorded on the appropriate form and in the patient's CRF. If the partner provides consent for follow-up of the pregnancy, she will be followed until the delivery of the child, and information on the delivery status of the mother and child will be forwarded to the sponsor no later than 8 weeks following the delivery date.

Any SAE occurring as a result of a post-study pregnancy that the investigator believes may have been caused by the study product or by a protocol procedure will be reported to the sponsor as described in Section 7.2.1.6.

8 STUDY COMMITTEES

A Data Safety Monitoring Board (DSMB) will be set up to oversee the safety of the patients enrolled in the study.

9 STATISTICAL ANALYSIS

9.1 Endpoints

9.1.1 Primary Endpoints

- Adverse events (AEs): Frequency, severity, time to onset, duration, and relatedness to study product
- Serious adverse events (SAEs): Frequency and relatedness to study product
- Number of discontinuations due to AEs

9.1.2 Secondary Endpoints

The time points for the efficacy assessments are defined below. Since the baseline measures are by definition those taken prior to the start of deferiprone therapy, "baseline" is defined differently for the two groups, as follows:

- **Group 1:** For patients who received deferiprone in LA38-0411, the baseline visit of that study will be treated as the baseline visit of LA38-EXT as well. Thus, Week 0 of the extension study will be Year 1 (i.e., the completion of one year of deferiprone treatment), Week 52 will be Year 2, and Week 104 will be Year 3.
- **Group 2:** For patients who received deferoxamine in LA38-0411, the start of the extension study (Week 0) will be treated as the baseline visit. For this group, therefore, Week 52 will be Year 1, and Week 104 will be Year 2.

Efficacy endpoints are provided below. For Group 1, the change from baseline to Year 1 is derived from study LA38-0411. For Group 2, there is no Year 3 of deferiprone treatment.

- The change from baseline to Year 1 (both groups; Group 1 data are from LA38-0411), from baseline to Year 2 (both groups), and from baseline to Year 3 (Group 1 only) in liver iron concentration (LIC), as measured by magnetic resonance imaging (MRI)
- The change from baseline to Year 1 (both groups; Group 1 data are from LA38-0411), from baseline to Year 2 (both groups), and (Group 1 only) from baseline to Year 3 in cardiac MRI T2*
- The change from baseline to Year 1 (both groups; Group 1 data are from LA38-0411 data), from baseline to Year 2 (both groups), and from baseline to Year 3 (Group 1 only) in serum ferritin
- Responder analysis, defined as the percentage of patients who show a ≥20% decline from baseline in LIC or serum ferritin or a >20% increase from baseline in cardiac MRI T2* at

Year 1 (both groups; Group 1 data are from LA38-0411), at Year 2 (both groups), and at Year 3 (Group 1 only)

9.2 Determination of Sample Size and Study Power

A planned total of 300 patients will be randomized in the LA38-0411 study to receive 1 year of either deferiprone or deferoxamine, and all patients who complete that study will be invited to enroll in the extension study.

9.3 Study Populations

Study populations intended for analysis will be defined as follows: Intent-to-Treat (ITT), Per-Protocol (PP), and Safety. The ITT population will represent the primary analysis population to evaluate all efficacy endpoints. The efficacy endpoints will also be analyzed for the PP population, which is the secondary analysis population.

9.3.1 Intent-to-Treat Population

The ITT population will include all randomized patients who received at least one dose of study drug and have a baseline and at least one post-baseline efficacy assessment.

9.3.2 Per Protocol Population

The Per-Protocol (PP) population will include all enrolled patients who complete the study, have no major protocol violations, and have an efficacy assessment at the end of the study. Prior to database lock, patients with major protocol violations will be reviewed and excluded, where appropriate, from the PP population. Major protocol violations will include (but not be limited to) the following:

- Patients who were not compliant with the treatment (<80% compliance)
- Patients who took iron chelator medications other than the assigned study medication during the course of the study

9.3.3 Safety Population

The safety population will include all enrolled patients who took at least one dose of study drug.

9.4 Data Analysis Plan

A separate detailed statistical analysis plan (SAP) will be prepared and approved before database lock. Any changes in the planned statistical methods after database lock will be documented in the final clinical study report.

9.4.1 Planned Analyses

9.4.1.1 Patient Disposition and Drug Exposure

Patient disposition will be summarized and presented, including the number and percentages of patients who were enrolled, received at least one dose of study medication, completed the study, and withdrew (including reasons for withdrawals). For each patient, the number of doses taken will be computed from the study drug dispensing and accountability eCRFs obtained at each visit. The extent of exposure to the study medication, the number of doses, and the total dose taken during the study will be summarized with descriptive statistics.

9.4.1.2 Patient Characteristics

Baseline characteristics for continuous variables will be summarized with descriptive statistics such as mean, standard deviation, minimum, median and maximum values. Baseline characteristics for discrete variables will be summarized with frequency tables.

9.4.1.3 Analysis of Efficacy

Changes in LIC, in cardiac MRI T2*, and in serum ferritin from baseline to Year 1(both groups; Group 1 data are from LA38-041), from baseline to Year 2 (both groups), and from baseline to Year 3 (Group 1 only) will be summarized with descriptive statistics, and will be tested against no change using a one-sample t-test. The changes in these 3 efficacy measures from the start of deferiprone therapy to the last visit of LA38-EXT in all patients, irrespective of whether deferiprone therapy was initiated in LA38-0411 or in LA38-EXT, will also be tested using a one-sample t-test. In addition, the percentages of responders will be tabulated for Year 1 (both groups; Group 1 data are from LA38-0411), for Year 2 (both groups), and for Year 3 (Group 1 only) of deferiprone therapy.

9.4.1.4 Analysis of Safety

The incidences of AEs and SAEs reported from the start of deferiprone therapy for all patients will be tabulated. For patients continuing on deferiprone, this time period will be from the start of LA38-0411 to the completion of LA38-EXT; for those switching to deferiprone, it will be from the start of LA38-EXT to the completion of LA38-EXT. AEs will be summarized by worst severity and by relationship to the study medication. Time to onset and duration of all SAEs, of AEs of special interest such as neutropenia, agranulocytosis, increased ALT, and arthralgia, and of additional AEs that will be determined at the end of LA38-0411, will be analyzed as follows: 1) the mean time to the first onset and the mean time to the last recurrence will be calculated, and 2) the mean duration for the first episode and the mean duration for any recurrent episodes, excluding the first episode, will be calculated for all SAEs and such AEs.

The percentage of discontinuations due to AEs will be calculated, and the AEs leading to discontinuation will be summarized in a frequency table.

Laboratory data (hematology and chemistry) will be summarized using descriptive statistics for continuous variables and frequency tables for discrete variables. The incidences of out-of-range data that are seen for two consecutive measures will be tabulated, and the changes from baseline to the end of study will be presented in shift tables.

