4.5.3 Treatment Interruptions

Study medication will be interrupted for ANY of the following reasons:

Infection, fever, or decrease in ANC:

- If the patient develops an infection during the study, deferiprone must be interrupted immediately and neutrophil count should be obtained and monitored more frequently (every 2 days if ANC <1.5 x 10⁹/L). Patients should be advised to report immediately to their physician any symptoms indicative of infection such as fever, sore throat, and flu-like symptoms. They will be provided with a thermometer, and instructed to seek immediate medical attention at a hospital or clinic if they experience fever (temperature >38.0° C/100.4°F). Body temperature may be measured at the mouth, axilla, or ear. Patients/legal guardians will be provided with an emergency services card with contact information, and will be advised to carry this card at all times. In presence of confirmed fever and/or infection, they will be required to have their neutrophil counts tested as soon as possible and no later than 24 hours after the symptoms of infection are detected. Therapy with deferiprone can be re-initiated once all symptoms have been resolved and it is deemed safe by the investigator.
- If temperature is >38.0°C/100.4°F and ANC is \le 0.5 x 10⁹/L, the following must be done:
 - Commence therapy with antibiotics immediately (treatment should depend on the site of the suspected infection and on local antibiotic policy)
 - Perform a chest x-ray, and collect blood and other relevant cultures (if possible, collect culture samples before initiating antibiotics)

• If the patient develops moderate neutropenia while on deferiprone, therapy must be interrupted immediately and neutrophil count must be obtained and monitored every 2 days. Therapy with deferiprone can be re-initiated once two successive ANCs are >1.5 x 10⁹/L and it is deemed safe by the investigator. The patient will be withdrawn from the study if the ANC remains <1.5 x 10⁹/L by the end of a 2-week period (14 days).

For definitions of and further detail on the management of neutropenia, see Section 7.2.1.8.1.

Increase in ALT:

If a patient whose ALT level was normal at baseline is confirmed to have serum ALT levels $\geq 5 \text{ x ULN}$ on 2 consecutive assessments, deferiprone treatment may be interrupted based on investigator judgment.

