6.3.4 Analysis of Safety

The incidences of AEs and SAEs reported from the start of deferiprone therapy for all patients will be tabulated. For patients continuing on deferiprone, this time period will be from the start of LA38-0411 to the completion of LA38-EXT; for those switching to deferiprone, it will be from the start of LA38-EXT to the completion of LA38-EXT. AEs will be summarized by worst severity and by relationship to the study medication. Time to onset and duration of all SAEs, of AEs of special interest such as neutropenia, agranulocytosis, increased ALT, and arthralgia: 1) the mean time to the first onset and the mean time to the last recurrence will be calculated, and 2) the mean duration for the first episode and the mean duration for any recurrent episodes, excluding the first episode, will be calculated for all SAEs and AEs of special interest.

The percentage of discontinuations due to AEs will be calculated, and the AEs leading to discontinuation will be summarized in a frequency table.

Laboratory data (hematology and chemistry) will be summarized using descriptive statistics for continuous variables and frequency tables for discrete variables. The incidences of out-of-range data will be tabulated, and the changes from baseline to the end of study will be presented in shift tables.

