14.3 Safety

14.3.1 Hematology

Figure 14.3.1.1 Mean line graph for hemoglobin over visit – Safety population

Figure 14.3.1.2 Proportion of patients with abnormal hemoglobin at each assessment – Safety population

Note: Similar graphs will be produced for total white blood cell (WBC), absolute neutrophil count (ANC), and platelets.

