Week 48	XXX	XX.X ± XX.X (xx, xx)	XXX	XX.X ± XX.X (xx, xx)	0xxxx
Week 49	XXX	XX.X ± XX.X (xx, xx)	XXX	XX.X ± XX.X (xx, xx)	0xxxx
Week 50	XXX	XX.X ± XX.X (xx, xx)	XXX	XX.X ± XX.X (xx, xx)	0xxxx
Week 51	XXX	XX.X ± XX.X (xx, xx)	XXX	XX.X ± XX.X (xx, xx)	0xxxx
Month 12	XXX	XX.X ± XX.X (xx, xx)	XXX	XX.X ± XX.X (xx, xx)	0xxxx
Month 15	XXX	XX.X ± XX.X (xx, xx)	XXX	XX.X ± XX.X (xx, xx)	0xxxx
Month 18	XXX	XX.X ± XX.X (xx, xx)	XXX	XX.X ± XX.X (xx, xx)	0xxxx
Month 21	XXX	XX.X ± XX.X (xx, xx)	XXX	XX.X ± XX.X (xx, xx)	0xxxx
Month 24	XXX	XX.X ± XX.X (xx, xx)	XXX	XX.X ± XX.X (xx, xx)	0xxxx
Month 27	XXX	XX.X ± XX.X (xx, xx)	XXX	XX.X ± XX.X (xx, xx)	0xxxx
Month 30	XXX	XX.X ± XX.X (xx, xx)	XXX	XX.X ± XX.X (xx, xx)	0xxxx
Month 33	XXX	XX.X ± XX.X (xx, xx)	XXX	XX.X ± XX.X (xx, xx)	0xxxx
Month 36	XXX	XX.X ± XX.X (xx, xx)	XXX	XX.X ± XX.X (xx, xx)	0xxxx

Note: Similar tables will be produced for total white blood cell (WBC), absolute neutrophil count (ANC), and platelets.

Data source: 16.2.9 Listing of hematology

Table 14.3.6.1.3 Shift table for hemoglobin in abnormal range at baseline vs last assessment:
DFP+DFP group

		Last Assessment				
		n (%)	Low	Normal	High	P-value (McNemar's test)
Baseline	Low	xx (xx)	xx (xx)	xx (xx)	0.xxxx	
	Normal	xx (xx)	xx (xx)	xx (xx)		
	High	xx (xx)	xx (xx)	xx (xx)		

Note: Similar tables will be produced for total white blood cell (WBC), absolute neutrophil count (ANC), and platelets.

Data source: 16.2.9 Listing of hematology

Table 14.3.6.1.4 Shift table for hemoglobin in abnormal range at baseline vs last assessment: DFO+DFP group

		Last Assessment				
		n (%)	Low	Normal	High	P-value (McNemar's test)
Baseline	Low	xx (xx)	xx (xx)	xx (xx)	0.xxxx	
	Normal	xx (xx)	xx (xx)	xx (xx)		
	High	xx (xx)	xx (xx)	xx (xx)		

Note: Similar tables will be produced for total white blood cell (WBC), absolute neutrophil count (ANC), and platelets.

Data source: 16.2.9 Listing of hematology

Table 14.3.6.2.1 Total protein at each assessment

	Treatment				
	DFP+DFP		DFO+DFP		
Visit	N	Mean ± SD (Min, Max)	N	Mean ± SD (Min, Max)	P-value (T-test)
Baseline	XXX	XX.X ± XX.X (xx, xx)	XXX	XX.X ± XX.X (xx, xx)	0xxxx
Month 1	XXX	XX.X ± XX.X (xx, xx)	XXX	XX.X ± XX.X (xx, xx)	0xxxx
Month 2	XXX	XX.X ± XX.X (xx, xx)	XXX	XX.X ± XX.X (xx, xx)	0xxxx
Month 3	XXX	XX.X ± XX.X (xx, xx)	XXX	XX.X ± XX.X (xx, xx)	0xxxx
Month 4	XXX	XX.X ± XX.X (xx, xx)	XXX	XX.X ± XX.X (xx, xx)	0xxxx
Month 5	XXX	XX.X ± XX.X (xx, xx)	XXX	XX.X ± XX.X (xx, xx)	0xxxx

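### The out-of-range laboratory incidence has no baseline condition and no direction, the SAP drops its confirmation rule, and no table shell defines it

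*Protocol*

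**What the plan says.** Protocol section 9.4.1.4 (Analysis of Safety) plans, for hematology and chemistry: "The incidences of out-of-range data that are seen for two consecutive measures will be tabulated". The same sentence adds shift tables from baseline to end of study.

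SAP section 6.3.4 reads: "The incidences of out-of-range data will be tabulated, and the changes from baseline to the end of study will be presented in shift tables". The two-consecutive condition is gone.

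The SAP table list (14.3.6.1 and 14.3.6.2) and the shells in section 17 contain values by visit, changes by visit and shift tables. None is an out-of-range incidence table. The nearest outputs are figures: Figure 14.3.1.2 is titled "Proportion of patients with abnormal hemoglobin at each assessment", and a note adds: "Similar graphs will be produced for total white blood cell (WBC), absolute neutrophil count (ANC), and platelets". Figure 14.3.2.2 does the same for chemistry, including ALT.

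The shift shells, for example "Shift table for hemoglobin in abnormal range at baseline vs last assessment: DFO+DFP group", cross Low/Normal/High at baseline with Low/Normal/High at the last assessment.

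Two rules elsewhere in the protocol are more specific. Section 7.2.1.8.1 states: "Patients taking deferiprone must be monitored for neutropenia, defined as a confirmed absolute neutrophil count (ANC) less than" 1.5 x 10^9/L, which is confirmed and in the low direction only. The ALT rule in section 4.5.3 begins: "If a patient whose ALT level was normal at baseline is confirmed to have serum ALT levels" of at least 5 x ULN, so it is tied to a normal baseline.

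**The concern.** Incidence means new occurrence. A count of patients with out-of-range values that takes no account of their status before the first dose mixes new abnormalities with those already present, which makes it closer to prevalence. This matters here because the study enrols patients with sickle cell disease or other anemias, and Protocol section 1.1.1 describes chronic anemia as part of the disease. Low hemoglobin at entry is expected. Raised ALT at entry is also possible: the only numeric ALT limit in the exclusion criteria (section 4.3) is an example at 5 x ULN or more, for Group 2 only and subject to the investigator's opinion.

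Direction matters most for ANC. Protocol section 1.3 names agranulocytosis as the most significant serious event with the drug. A summary that pools high and low counts as abnormal does not show the direction of interest.

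Safety is the primary objective. A laboratory value becomes an adverse event only if the investigator judges it clinically significant (sections 7.2.1.1 and 7.2.2). The out-of-range tabulation is the summary that does not depend on that judgment, so its definition needs to be sound.

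**Working it through.** The plan states no figure on this point, so there is nothing to reproduce. The check compares the planned outputs and then illustrates how the undefined elements behave. All rates in steps 2 and 3 are assumptions, not estimates for this trial.

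**1. What each planned laboratory output can show**

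| Output | Baseline status | Direction | Any time on drug | Confirmed |
|---|---|---|---|---|
| Protocol 9.4.1.4 incidence | not stated | not stated | yes, as worded | two consecutive |
| SAP 6.3.4 incidence | not stated | not stated | yes, as worded | no |
| Figures 14.3.1.2 and 14.3.2.2 | no | no | visit by visit | no |
| Shift tables | yes | yes | last assessment only | no |

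No row has both baseline status and any time on drug. A patient with normal ANC at baseline, a low count in mid-study that resolves, and a normal last count appears in the shift table as Normal to Normal. The by-visit tables give a minimum and maximum, but do not show whether the extreme value was new for that patient.

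**2. Effect of omitting the baseline condition**

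Let b be the share out of range at baseline and remaining so, and r the new-onset rate among the rest. The unrestricted count gives b + (1 - b)r; the restricted count gives r. With r = 5% (assumed):

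- b = 5%: 0.05 + 0.95 x 0.05 = 9.75%; 51% of those counted were abnormal at entry (0.05/0.0975)
- b = 20%: 0.20 + 0.80 x 0.05 = 24%; 83% abnormal at entry
- b = 50%: 0.50 + 0.50 x 0.05 = 52.5%; 95% abnormal at entry
- b = 95%: 0.95 + 0.05 x 0.05 = 95.25%; 99.7% abnormal at entry

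Varying r from 2% to 10% at b = 50% moves the count only from 51% to 55%. Once b is large, the count barely responds to the drug effect.

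**3. Effect of direction and confirmation**

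Scheduled hematology counts in the extension alone: Group 1, 24 monthly; Group 2, 26 weekly + 13 biweekly + 12 monthly = 51. Assume independent counts with 2.5% beyond each limit. A single flag by chance has probability 1 - (1 - p)^k. For two consecutive flags, carry forward the probability of no run so far, split by whether the last count was flagged.

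| Chance flag | 24 counts | 51 counts |
|---|---|---|
| Any single flag, either direction (p = 0.05) | 70.8% | 92.7% |
| Any single low flag (p = 0.025) | 45.5% | 72.5% |
| Two consecutive, any direction | 5.4% | 11.3% |
| Two consecutive, same direction | 2.8% | 5.9% |
| Two consecutive low | 1.4% | 3.0% |

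Dropping confirmation has the largest effect. The second and fifth rows also show that a direction-specific count without confirmation would still be dominated by chance. Every row depends on the number of tests. Because Group 1's deferiprone period also includes LA38-0411, its full number of counts exceeds 24.

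**The case against.** The strongest reply is that the texts are silent rather than wrong: they do not say that patients abnormal at entry are to be counted, and a programmer might restrict the count sensibly. That is fair as far as it goes. But no shell or definition would lead the programmer there, and the plain wording does not exclude those patients.

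The second reply is that the important signals are covered elsewhere, and this largely stands. Neutropenia is low-only, confirmed and graded. Neutropenia, agranulocytosis and increased ALT are adverse events of special interest, with time to onset and duration analysed from the start of deferiprone. Conditions already present that do not worsen are not adverse events (section 7.2.1.1). A reader might infer that disease abnormalities and high ANC counts will be reported as adverse events on deferiprone. The documents do not support that: high counts cannot enter the neutropenia results.

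Third, the figures are labelled as by-visit proportions and do not claim to be incidence. That is correct; the criticism of them is limited to pooling low with high.

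Finally, a reader might try to size the inflation from the adverse-reaction table in section 1.3, such as 7.6% for increased ALT or 6.9% for neutropenia. Those are rates of reactions judged at least possibly related, not of out-of-range values, so the comparison is not valid. The ALT rule in section 4.5.3 governs treatment interruption; it shows that the protocol recognises baseline status, but it is not a precedent for the analysis.

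**Conclusion.** The concern holds for the laboratory summaries. The out-of-range incidence lacks a baseline condition and a direction in both documents, the SAP removes the protocol's confirmation rule, and no table or shell supplies the missing definition. The shift tables close the gap only at the last assessment. As planned, no laboratory summary isolates a new, direction-specific abnormality occurring at any time on deferiprone.

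The adverse-event results are not affected, and neutropenia and increased ALT remain captured there, subject for ALT to the investigator's judgment of clinical significance.

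No magnitude can be given for this trial, because the documents report no baseline shares. The percentages in the working show the mechanism under assumed rates and independent counts. Repeated counts in one patient are likely to be correlated, which would change the chance-flag figures.

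**What to change.** In Protocol section 9.4.1.4 and SAP section 6.3.4, replace the sentence with a definition along these lines:

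- Tabulate treatment-emergent low and treatment-emergent high values separately for each parameter.
- Count a patient when two consecutive measures after the first deferiprone dose are out of range in the same direction. This restores the protocol's condition in the SAP.
- Use as denominator the patients not out of range in that direction at the last pre-deferiprone value (LA38-0411 baseline for Group 1, Week 0 for Group 2).
- Show on a separate line the number already out of range at baseline. Report worsening by grade only where the plan defines a grade, as it does for ANC.
- Add a table shell, and split Figures 14.3.1.2 and 14.3.2.2 into low and high.
- Add a note that Groups 1 and 2 are tested at different frequencies, so differences between them partly reflect the number of tests.

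The cost is wording, one shell and derived baseline and direction flags; no new data are needed. There are two downsides. Denominators will differ by parameter. For chemistry, scheduled extension measures are 26 weeks apart (Weeks 0, 26, 52, 78, 104), so the two-consecutive rule will not count a rise seen at only one of them; the by-visit figures, once split by direction, would still display it.
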